6.3.1.7 Subject Drug Compliance

Subjects will be asked about drug compliance and any adverse events he or she may experience during clinic visits. Any discrepancies in drug accountability will be clarified with the subject.

6.3.1.8 Disease Assessment

Contrast enhanced imaging studies (CT or MRI) will be performed at screening and every 8 weeks beginning Cycle 3/Day 1. All sites of known disease must be assessed. CT modalities should be done according to standard of care for the subject's disease.

6.4 Post-Treatment Period

6.4.1.1 Safety Follow-Up

Subjects will return to the study site 30 to 37 days after their last dose of study drugs to complete end-of-study safety assessments.

Laboratory and physical examinations will be performed. Remaining study treatment will be returned by the subject, and treatment compliance via subject drug diaries will be documented. Additional follow-up will occur for subjects with AEs related to study treatment that are ongoing at the time of this visit, and for subjects with SAEs related to study treatment that occur after the time of this visit.

6.5 Survival Follow-Up

Subjects will be followed every 3 months for up to 2 years after treatment discontinuation for survival via medical record review or phone call to the subject and/or next of kin.

6.6 Correlative Studies

HGF and its receptor, c-Met (also known as Met and MET), are also overexpressed in PDAC. c-Met also heterodimerizes with EGFR, and EGFR-Met cross-talk may contribute to chemoresistance. Np-1 and Np-2, which are transmembrane proteins that act as co-receptors for VEGF-A, HGF, and class 3–secreted semaphorins, are also overexpressed in PDAC, and Np-1 associates with Met, enhancing HGF's ability to promote migration and invasion in pancreatic cancer cells (PCCs), as previously reported by us. Np-1, which does not associate with EGFR, can signal via integrin beta 1 (ITG- β 1) to promote PCC invasion and survival. ITG- β 1, which is also overexpressed in PDAC, can enhance EGFR signaling. Together, these observations point to a previously unrecognized signaling node in PDAC that consists of Met/EGFR/Np-1/2, and ITG- β 1. In this proposal, we will test the hypothesis that it is possible to target this signaling node by dual inhibition of Met with cabozantinib and EGFR with erlotinib.

CONFIDENTIAL

Based on the above, we will analyze tumor tissue to assess expression of c-Met and EGFR by RT-qPCR and immunohistochemistry. Immunostaining will be conducted by Indiana University Health Department of Pathology on baseline samples and in the [name] laboratory for samples collected post-treatment using the same standard operating procedures (SOPs). SOPs will include same antibodies and antibody titers, and same antigen exposure procedures. The advantages of using the RT-qPCR and immunohistochemistry approaches is that they are easy to execute rapidly and may yield important information for trial design and interpretation. By rapidly performing RT-qPCR for HGF, c-Met, and EGFR, we will be able to accurately evaluate which PDAC samples express high levels of all three transcripts, and consider these patients as candidate for the clinical trial, even before performing the more sophisticated studies on the tumors as outlined above. In addition, we will assess expression of Np-1, ITG-b1, p-EGFR and p-c-Met by immunostaining and/or immunofluorescence.

We will perform contrast enhanced CT or MRI every 8 weeks with additional correlative studies on blood and tissue collected at baseline (pre-treatment) and Cycle 1/Day 15 (post-treatment) to measure Met and EGFR mRNA by qPCR, blood collection to assay plasma HGF and soluble Met receptor, and to evaluate Met and EGFR total phosphoprotein levels by electro-luminescent 2-site immunoassays in tissue to determine if these assays can serve as predictors of response to therapy.

All patients must have archival tissue for EGFR and c-Met expression testing by immunohistochemistry (IHC) as only patients with a test score of 2+ for both markers will be eligible to participate in this trial. Patients will be asked for archival tissue during the screening period (i.e. at baseline). It is anticipated that most patients who may be eligible for this study will have archival tissue available for screening. Patients without archival tissue are ineligible. Tumor tissue is required pre-treatment as part of study eligibility criteria to test for EGFR and c-MET expression. KRAS will also be tested if previous KRAS testing was not done or results are unknown AND there is adequate tissue available from tissue collected at screening. Archival tissue obtained may come from previous EUS or CT-guided biopsies or surgical resection. FNA cores are acceptable. Primary lesion tissue (typically obtained via EUS-guided biopsy or surgical resection) is preferred; however, metastatic lesion tissue may also be used (typically obtained via CT-guided biopsy). Only samples collected from eligible patients during the screening period will be utilized for the correlative studies which are outlined in this trial. Tissue samples collected from ineligible patients during screening will be discarded.

CONFIDENTIAL

Approximately 20 ml of blood will be collected at baseline (during screening period or prior to first administration of study drug on Cycle 1/Day 1) and beginning Cycle 1/Day 15 and every 4 weeks thereafter (i.e. Cycle 2/Day 1, Cycle 3/Day 1, Cycle 4/Day 1, etc.). Only samples collected from eligible patients during the screening period will be utilized for the correlative studies which are outlined in this trial. Blood samples collected from ineligible patients during screening will be discarded.

Complete details regarding tissue and blood collection, processing, transfer and storage information for these correlative studies can be found in the Laboratory Manual for this study.

7 SAFETY

7.1 Definitions of Adverse Events

7.1.1 Adverse Events

An AE is any untoward medical occurrence in a patient or clinical investigation subject who has been enrolled in a clinical study and who may have been given an investigational product, regardless of whether or not the event is assessed as related to the study treatment. An AE can therefore be any unfavorable and unintended sign (including an abnormal laboratory finding), symptom, or disease temporally associated with the use of an investigational product, regardless of whether or not the event is assessed as related to the investigational product. Pre-existing medical conditions that worsen during a study should be recorded as AEs. Abnormal laboratory values, ECG findings, or vital signs are to be recorded as AEs if they meet the criteria described in Section 4.3 and 4.4.

All untoward events that occur after patient begins study treatment through 30 after the decision to discontinue study treatment (or the date the subject is deemed to be a screen failure) are to be recorded by the investigational site. This requirement includes AEs from unscheduled as well as scheduled visits.

7.1.2 Suspected Adverse Reactions (SAR)

Suspected adverse reaction is any adverse event for which there is a reasonable possibility that the drug caused the adverse event. For the purposes of IND safety reporting, ‘reasonable possibility’ means there is evidence to suggest a causal relationship between the drug and the adverse event. A suspected adverse reaction implies a lesser degree of certainty about causality than adverse reaction, which means any adverse event caused by a drug. Suspected adverse reactions are the subset of all adverse events for which there is a reasonable possibility that the drug caused the event.

CONFIDENTIAL

Examples of types of evidence that would suggest a causal relationship between the drug and the adverse event:

- A single occurrence of an event that is uncommon and known to be strongly associated with drug exposure (e.g., angioedema, hepatic injury, Stevens-Johnson Syndrome).
- One or more occurrences of an event that is not commonly associated with drug exposure, but is otherwise uncommon in the population exposed to the drug (e.g., tendon rupture).
- An aggregate analysis of specific events observed in a clinical trial (such as known consequences of the underlying disease or condition under investigation or other events that commonly occur in the study population independent of drug therapy) that indicates those events occur more frequently in the drug treatment group than in a concurrent or historical control group.

7.1.3 Adverse Reaction (AR)

An adverse reaction is any adverse event caused by a drug. Adverse reactions are a subset of all suspected adverse reactions where there is reason to conclude that the drug caused the event.

7.1.4 Serious Adverse Events

The SAE definition and reporting requirements are in accordance with the International Conference of Harmonisation (ICH) Guideline for Clinical Safety Data Management: Definitions and Standards for Expedited Reporting, Topic E2A.

An SAE is defined as any untoward medical occurrence that at any dose:

- Result in death;
- Is immediately life-threatening (i.e., in the opinion of the investigator, the AE places the subject at immediate risk of death; it does not include a reaction that, had it occurred in a more severe form, might have caused death);
- Requires inpatient hospitalization ≥ 24 hours or prolongation of existing hospitalization
 - NOTE: Hospitalizations that are not considered SAEs are:
 - Hospitalization planned prior to first administration of study drug
 - Hospitalization for less than 24 hours
 - Hospitalization for elective treatment of a pre-existing condition unrelated to the study medication
- Results in persistent or significant disability or incapacity:

CONFIDENTIAL

- Note: The term “disability” refers to events that result in a substantial disruption of a subject’s ability to conduct normal life function.
- Is a congenital anomaly or birth defect;
- Is an important medical event (IME):
 - Note: The term “important medical event” refers to an event that, based upon appropriate medical judgment, may not be immediately life-threatening or result in death or hospitalization, but may jeopardize the subject or require intervention to prevent one of the other serious outcomes listed under the definition of SAE. Examples of IMEs include intensive treatment in an emergency room or at home for allergic bronchospasm; blood dyscrasias, or convulsions that do not result in hospitalization; or development of product dependency or product abuse.
- Pregnancy
 - Pregnancy of a female subject during the study or within 30 days after the last dose of study drug should be reported via an SAE report. Additional details regarding pregnancy can be found in Section 6.3.3.

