7.2.2 Reporting to Exelixis

7.2.2.1 SAEs

As soon as an investigator becomes aware of an AE that meets the definition of ‘serious,’ this should be documented to the extent that information is available.

- IUSCC shall notify Exelixis within twenty-four (24) hours of making such discovery by submitting a completed SAE report form and any other pertinent SAE information as indicated on the SAE reporting form;
- The SAE reporting form must be submitted to Exelixis even if it is not felt to be drug related;
- Pregnancy (for a subject or for the partner of a subject), although not itself an SAE, should also be reported on a pregnancy form and be followed up to determine outcome, including spontaneous or voluntary termination, details of birth, and the presence or absence of any birth defects or congenital abnormalities;
- SAEs that must be recorded on an SAE Reporting form include the following:
 - all SAEs that occur after informed consent and through 30 days after the decision to discontinue study treatment (or the date the subject is deemed to be a screen failure);
 - any SAEs assessed as related to study treatment or study procedures, even if the SAE occurs more than 30 days after the decision to discontinue study treatment;

CONFIDENTIAL

- although most hospitalizations necessitate reporting of an SAE, some hospitalizations do not require SAE reporting, as follows: elective or previously scheduled surgeries or procedures for pre-existing conditions that have not worsened after initiation of treatment (e.g., a previously scheduled ventral hernia repair); pre-specified study hospitalizations for observation; or events that result in hospital stays of fewer than 24 hours and that do not require admission (e.g., an emergency room visit for hematuria that results in a diagnosis of cystitis and discharge to home on oral antibiotics). SAEs must, however, be reported for any surgical or procedural complication resulting in prolongation of the hospitalization.

IUSCC will report to Exelixis all SAEs that are sent to the FDA at the time of submission to the FDA. Follow-up information will be provided to Exelixis as reasonably requested. Send SAE reports on the MedWatch Report Form to:

Exelixis Drug Safety
[contact]
Email: [contact]

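### Sections 7.1.4 and 7.2.2.1 exempt elective and planned admissions on different conditions, so they disagree on some stays for a condition that worsened on treatment

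*Combined protocol and SAP*

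**What the plan says.** Section 7.1.4 makes an event serious if it "Requires inpatient hospitalization ≥ 24 hours or prolongation of existing hospitalization". A note then lists exceptions, introduced by "NOTE: Hospitalizations that are not considered SAEs are". Apart from stays under 24 hours, the exceptions are "Hospitalization planned prior to first administration of study drug" and "Hospitalization for elective treatment of a pre-existing condition unrelated to the study medication". The first has no further condition. The second depends on relatedness. Neither mentions worsening.

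Section 7.2.2.1, on reports to the drug supplier, starts from the position that most hospital stays are reported as SAEs and lists those that are not. The relevant exemption covers "elective or previously scheduled surgeries or procedures for pre-existing conditions that have not worsened after initiation of treatment". It depends on worsening and does not mention causality. The same section adds: "The SAE reporting form must be submitted to Exelixis even if it is not felt to be drug related".

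Section 7.1.1 settles the status of the underlying event: "Pre-existing medical conditions that worsen during a study should be recorded as AEs". Section 8.3 leaves both seriousness and relatedness to the investigator. No section says which of the two exemption lists governs.

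**The concern.** Seriousness describes what happened to the patient; relatedness is an opinion about why. The protocol treats them as separate attributes in sections 3.2, 6.3.1.1 and 8.3, and 7.2.2.1 wants SAE forms whatever the attribution. The elective-admission bullet in 7.1.4 joins the two: a worsened condition that leads to an elective stay is or is not serious according to the causality opinion. The planned-admission bullet goes further, because a stay arranged before first dose remains exempt even if the condition deteriorated on treatment in the meantime.

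What is at stake is consistent SAE capture. SAE status triggers the 24-hour report to the supplier (7.2.2.1), OnCore entry within one business day (9.6), the SAE reviews by the DSMC and its chair (9.1, 9.4), and the SAE listings and tables (8.8). Section 7.2.4 lets the supplier upgrade the investigator's assessment of an SAE, which presupposes that a form was sent. In a single-arm trial no control group helps to separate drug effect from disease, so a single causality opinion is a weak filter on what is counted.

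**Working it through.** The documents state no figure on this point, so the check is to apply both rules to the same cases. Take an inpatient stay of 24 hours or more for elective or previously scheduled treatment of a pre-existing condition, with no other seriousness criterion met (for example, not an important medical event).

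| Planned before first dose | Worsened on treatment | Judged related | 7.1.4 | 7.2.2.1 | Agree? |
|---|---|---|---|---|---|
| No | No | No | Not an SAE | Exempt | Yes |
| No | Yes | No | Not an SAE | Not exempt | **No** |
| No | Yes | Yes | SAE | Not exempt | Yes |
| No | No | Yes | Not excluded | Exempt | No (reverse direction; unlikely in practice) |
| Yes | No | Either | Not an SAE | Exempt | Yes |
| Yes | Yes | Either | Not an SAE | Not exempt | **No** |

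Rows two and three differ only in the causality opinion, and that alone changes the status under 7.1.4. In row six the timing of the plan overrides the worsening.

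Not exempt under 7.2.2.1 means reportable by inference: the section makes reporting the usual course for hospital stays and this stay is not among its exceptions. It does not say outright that stays for worsened conditions must be reported.

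Size per patient, from the planned 37 patients and the ceiling of 40 in section 8.5, for a patient with no other SAE:

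- 1/40 = 0.025, or 2.5 percentage points
- 1/37 = 0.027, or 2.7 percentage points

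The number of such patients cannot be derived from the documents.

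**The case against.** The strongest reply is that 7.2.2.1 opens with an AE that already meets the definition of serious. On that reading 7.1.4 is applied first, and a stay that it excludes never reaches 7.2.2.1. This is a possible reading, but it leaves the worsening condition in 7.2.2.1 with no effect in rows two and six, and the protocol does not state the order. One can also argue the opposite: the worsened condition is itself an AE under 7.1.1, and if it requires admission it meets the main hospitalization criterion. That two defensible readings give opposite answers is the problem.

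A reader might infer more than the documents support:

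- **That the collection window adds a further contradiction.** Section 7.2.2.1 collects "all SAEs that occur after informed consent and through 30 days after the decision to discontinue study treatment". This fixes when SAEs are collected, not what an SAE is, so it does not conflict with an exemption tied to first dose.
- **That 15-day IND reports are lost.** Under 7.1.2 and 7.2.3.1 a 15-day report needs a reasonable possibility that the drug caused the event. An event judged unrelated fails that test whichever list is used. The 7-day report and prompt IRB reporting likewise require an association with treatment or the research.
- **That the event goes unseen.** It is still recorded as an AE (7.1.1) and summarised among AEs that started or worsened on treatment (8.8). Weekly safety meetings (section 9) and the semi-annual DSMC review of toxicity (9.1) do not depend on SAE status.
- **That SAE incidence shifts by several patients' worth.** The documents give no basis for any number of affected patients.

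Each of these limits stands. None removes the disagreement between the two lists.

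**Conclusion.** The two exemptions conflict and need reconciling. The conflict is confined to elective or pre-planned inpatient stays of 24 hours or more, for a pre-existing condition that worsened on treatment, that meet no other seriousness criterion and were either judged unrelated or planned before first dose. For these, SAE status depends on which section the site follows and, for elective stays not planned before first dose, on the causality opinion.

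The effect falls on supplier reporting, OnCore SAE capture, the DSMC's SAE review and the SAE tables: 2.5 to 2.7 percentage points of SAE incidence per affected patient, assuming 37 to 40 treated patients and no other SAE in that patient. For worsened conditions, following 7.1.4 can only lower the count. The reverse case in row four exists on paper, so a general claim of downward bias would be too strong. No decision rule uses SAE incidence, and the response endpoint and two-stage design are untouched. The reason to act is that an operative safety rule should give one answer and the correction is small.

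**What to change.** In the 7.1.4 note, replace the elective-treatment and planned-admission bullets with a single exemption on the 7.2.2.1 condition, "elective or previously scheduled surgeries or procedures for pre-existing conditions that have not worsened after initiation of treatment", and drop the relatedness qualifier. Worsening, not causality or the date of planning, then decides the exemption in both sections.

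Leave three things as they are: the exemption for stays under 24 hours, the 7.2.2.1 exemption for pre-specified observation stays, and the 7.2.2.1 sentence on procedural complications that prolong a stay. The new text should replace only the two bullets. Wording it as the sole ground for exemption would delete the first two of these by accident.

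The cost is about two lines of protocol text and a few more SAE forms.

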7.1.5 Unexpected Adverse Events

An adverse event or suspected adverse reaction is considered “unexpected” if it is not listed in the Reference Safety Information section (Appendix K) of the Investigator’s Brochure (cabozantinib), Adverse Reactions section of the Package Insert (erlotinib), or is not listed at the specificity or severity that has been observed; or, if an investigator brochure is not required or available, is not consistent with the risk information described in the general investigational plan or elsewhere in the current application, as amended. For example, under this definition, hepatic necrosis would be unexpected (by virtue of greater severity) if the investigator brochure referred only to elevated hepatic enzymes or hepatitis. Similarly, cerebral thromboembolism and cerebral vasculitis would be unexpected (by virtue of greater specificity) if the investigator brochure listed only cerebral vascular accidents. "Unexpected," as used in this definition, also refers to adverse events or suspected adverse reactions that are mentioned in the investigator brochure as occurring with a class of drugs or as anticipated from the pharmacological properties of the drug, but are not specifically mentioned as occurring with the particular drug under investigation.

This definition relies entirely on the adverse events or suspected adverse reactions listed in the investigator brochure for the particular drug under investigation (or elsewhere in the general investigational plan if an investigator brochure is not required or available) as the basis for determining whether newly acquired information generated from clinical trials or reported from other sources is unexpected. This means that events not listed for the particular drug under

CONFIDENTIAL

investigation in the investigator brochure are considered “unexpected” and those listed are considered “expected.” When new adverse event information is received, it is the PI’s responsibility to determine whether the event is “unexpected” for IND safety reporting purposes. In the clinical trial setting, there has been some confusion with the term “expected” as it has been used to mean “anticipated” for the disease being treated or population being studied rather than “listed in the investigator brochure.” For example, some adverse events can be anticipated to occur as a result of a disease or in an older population (e.g., cancer-related deaths in a cancer trial, strokes or acute myocardial infarctions in an older population). However, for reporting purposes, these anticipated events are not “expected” because they are not listed in the investigator brochure (i.e., the test drug is not suspected or known to cause them).

Adverse events listed in the investigator brochure as occurring with members of the same class of drugs, or as anticipated from the pharmacological properties of the drug, would be considered unexpected until they have been observed with the drug under investigation. For example, although angioedema is anticipated to occur in some patients exposed to drugs in the angiotensin-converting enzyme (ACE) inhibitor class and angioedema would be described in the investigator brochure as a class effect, a case of angioedema observed with the drug under investigation should be considered unexpected for reporting purposes until it is included in the investigator brochure as occurring with the drug under investigation.

